14. CLINICAL MANAGEMENT

14.1 Clinical Management of Adverse Events

14.1.2. Drug toxicity

Criteria for participant management, dose interruptions, dose adjustments and discontinuation, or changes in treatment will be described only for toxicities attributable to study drugs (either SOF/VEL or SOF/DAC). The grading system for drug toxicities is located in the DAIDS AE Grading Table (see **Section 13.2.2**).

NOTE: The PIs must be notified via e-mail within 7 days regarding toxicities that result in a change in study regimen

It is possible that some participants will experience transient or prolonged AEs during the study. In this trial, the scheduled on-treatment visits are as per the standard of care of treatment delivery in India. In addition, participants can come into the study site at any time to one of the study clinicians in order for AEs to be identified. Detailed data on AEs that are reported at study visits and inbetween study visits will be collected in the eCRFs.

14.1.3. Management of side effects of SOF/VEL and SOF/DAC

There are no signature abnormalities associated with SOF/VEL or SOF/DAC. If an SAE occurs, the site clinician should contact one of the two protocol physicians and has the option to discontinue study treatment. However, prior to the discontinuation of study drugs, the study PIs should be notified by email within 7 days of its occurrence.

Participants who meet any of the following laboratory criteria should stop treatment with SOF/VEL or SOF/DAC:

- Confirmed elevation of ALT and/or AST >5 x entry values measured while on study treatment measured at planned or unplanned study visits.
- Confirmed direct bilirubin 3 x ULN and >2.0 mg/dL
- Any Grade 3 or greater rash associated with constitutional symptoms assessed as related to treatment with SOF/VEL or SOF/DAC.
- Any Grade 4 event assessed as related to treatment with SOF/VEL or SOF/DAC.

Dose modification of SOF/VEL and SOF/DAC will not be allowed in the study. If SOF/VEL or SOF/DAC is discontinued for toxicity reasons, it should not be restarted.

NOTE: Grades 1 and 2 AEs associated with SOF/VEL and SOF/DAC require no change in study treatment.

14.2 Pregnancy

Because there is insufficient data on the safety of SOF/VEL and SOF/DAC during pregnancy, pregnancy will result in the discontinuation of study medication and initiation of counseling regarding the lack of information on safety of SOF/VEL or SOF/DAC in pregnancy. While there was a recent demonstration of the safety of SOF/ledipasvir among pregnant women enrolled at 23-24 weeks of gestation,⁹⁵ the women enrolled in this study will be receiving different regimens. Moreover, if women become pregnant during the course of this study, it is likely that their HCV treatment exposure would be within the first trimester of their pregnancy and the safety of the medications during that time period has not yet been established.

Participants in whom pregnancy is suspected should receive a pregnancy test during a study visit. Additionally, participants who suspect pregnancy or become pregnant should contact the site to schedule an unplanned study visit (only up to week 24) and will be followed on study/off-treatment until study completion. A visit following the end of pregnancy will be conducted for evidence of AEs in the participant, and an outcome eCRF will be completed. Male participants whose partners become pregnant will continue treatment.

If a female participant has completed the study or chooses to discontinue from the study before the end of the pregnancy, site staff will request permission to contact her regarding pregnancy outcomes at the end of pregnancy. If the information is obtained, pregnancy outcomes will be submitted on an eCRF at the end of the pregnancy.

Pregnancy and pregnancy outcome will be recorded on the eCRFs. Pregnancy outcomes will also be reported to the Drug Controller General India.

14.3 Treatment Failure

Participants in the trial who fail treatment will be referred to the nearest government hospital/program for possible retreatment. Retreatment will not be offered through the ICC.

14.4 Criteria for Discontinuation

14.4.1. Permanent and premature treatment discontinuation

Potential reasons for permanent or premature discontinuation of study treatment (SOF/VEL or SOF/DAC) are:

- Drug-related toxicity (see Section 14.1.2).
- Requirement for prohibited concomitant medications (see Section 11.2.4).
- Pregnancy in a female participant.
- Breastfeeding.
- Completion of treatment as defined in the protocol.
- Participant request to discontinue treatment for any reason.
- Clinical reasons believed life threatening by the physician, even if not addressed in the drug toxicity section of the protocol.

NOTE: It is important to determine whether the treatment discontinuation is primarily due to an AE, lack of efficacy, or other reason and record this in the eCRF.

14.4.2. Premature study discontinuation

Potential reasons for permanent or premature discontinuation of study participation are:

- Request by the participant to withdraw.
- Request of a study clinician if s/he thinks the study is no longer in the best interest of the participant.
- At the discretion of the IRB/Ethics Committee, National Institute of Allergy and Infectious Disease (NIAID), Office for Human Research Protections (OHRP), other government agencies as part of their duties, investigator.

The reason for premature study discontinuation will be recorded in an eCRF.

15. STATISTICAL CONSIDERATIONS

15.1 Overview and General Design Issues

The primary objective of the protocol is to evaluate whether HCV treatment outcomes (sustained virologic response) in HCV mono- and HIV/HCV co-infected PWID can be optimized by tailoring treatment support in 7 PWID-focused integrated HIV/HCV prevention/treatment centers. This is an unblinded individually randomized trial with an unbalanced allocation approach. An algorithm (based on early ART refills/HIV viral suppression) will be used to triage clients into two strata: minimal and elevated risk for failure. Using an unbalanced randomization approach, the goal is to assess the efficacy of low, medium and high intensity treatment support strategies within the two strata of risk (minimal and elevated) and overall sample. Eligible study participants include PWID clients who are eligible for HCV treatment in one of 7 integrated HIV/harm reduction centers across India. Study staff and participants will be blinded to whether participants were designated as minimal or elevated risk according to the prediction algorithm.

The primary outcome of this trial is SVR which will be assessed 10-60 weeks after treatment completion. All participants who achieve the primary outcome and those HIV co-infected will be followed for up to an additional 2.5 years to measure secondary outcomes of HCV reinfection and HIV viral suppression. The results from this trial will be used to guide programs in optimizing HCV treatment outcomes among PWID.

15.2 Study Endpoints

15.2.1. Primary endpoint(s)

Sustained virologic response (SVR) defined as HCV RNA < lower limit of quantification (LLOQ) 10 – 60 weeks after completion of treatment (cure).

15.2.2. Secondary endpoint(s)

- 1. Treatment completion defined as completing the prescribed course of treatment (12/24 weeks)
- 2. Treatment adherence to study treatment as self-reported by study participants
- 3. HCV reinfection defined as testing positive for HCV Core Ag after achieving SVR
- 4. HIV viral suppression among HIV/HCV coinfected participants defined as HIV RNA less than LLOQ (HIV RNA <150 copies/ml)

15.3 Study Objectives and Hypothesis/Hypotheses

15.3.1. Primary objective / hypotheses

Primary objective: To evaluate whether the intensity of treatment adherence support affects sustained virologic response rates in HCV mono- and HIV/HCV co-infected participants receiving DAAs in PWID-focused centers

Hypotheses:

- Among PWID at elevated risk for treatment failure, PWID receiving the high intensity intervention will have significantly higher SVR than those receiving either the medium or the low intensity interventions.
 - 1a. Among PWID at minimal risk for treatment failure, PWID receiving either the high or the medium intensity intervention will have significantly higher SVR than those receiving the low intensity interventions.

The formal null hypothesis is no difference in SVR and the alternate is a difference in SVR. The trial is designed for superiority assessment; however, if there is failure to detect a statistically significant difference between support strategies across any particular stratum, a lesser objective of interest is non-inferiority with a pre-specified non-inferiority margin.

15.3.2. Secondary objectives / hypotheses

15.3.2.1. To evaluate whether the intensity of treatment adherence support affects HCV treatment completion rates.

Hypothesis: Among PWID at elevated risk for treatment failure, PWID receiving the high intensity intervention will have significantly higher treatment completion than those receiving either the medium or the low intensity interventions.

Hypothesis: Among PWID at minimal risk for treatment failure, PWID receiving either the high or the medium intensity intervention will have significantly higher treatment completion than those receiving the low intensity interventions.

15.3.2.2. To evaluate whether the intensity of treatment adherence support affects HCV treatment adherence.

Hypothesis: Among PWID at elevated risk for treatment failure, PWID receiving the high intensity intervention will have significantly higher adherence than those receiving either the medium or the low intensity interventions.

Hypothesis: Among PWID at minimal risk of treatment failure, PWID receiving either the high or the medium intensity intervention will have significantly higher adherence than those receiving the low intensity intervention.

15.3.2.3. To estimate the incidence and correlates of HCV reinfection among HCV mono- and HIV/HCV coinfected PWID who achieve HCV cure.

Hypothesis: HCV reinfection will be lower among clients who have higher attendance at OAT programs.

15.3.2.4. To evaluate the impact of HCV cure on HIV viral suppression among HIV/HCV coinfected PWID.

Hypothesis: Among HIV/HCV co-infected PWID, HIV viral suppression will be higher after achievement of HCV cure.

15.4 Sample Size Considerations

The anticipated sample size for this trial is 3,000 with approximately 420 recruited at each site over an 18-24 month period. Approximately 15-20 persons per month per site will be recruited. Recruitment may be unbalanced across the sites due to larger client volume at some sites. Sample size calculations were based on the primary outcome: sustained virologic response (SVR) defined as HCV RNA < lower limit of quantification (LLOQ) 10 to 60 weeks after completion of treatment (cure) and an intention to treat analysis. The trial is defined for superiority assessment; however, if no statistically significant difference between support strategies is detected within a specific stratum, a lesser objective of interest is non-inferiority with a pre-specified non-inferiority margin.

ELEVATED RISK STRATUM	N=1500 total (750 high intensity, 500 medium intensity, 250 low intensity)		N=1225 total (intensity, 410 intensity, 200		N=1000 total (500 high intensity, 333 medium intensity, 167 low intensity)		
SVR in PWID	RR comparing RR comparing		RR RR comparing		RR	RR comparing	
receiving	high to low	high to medium	comparing	high to	comparing	high to	
low/medium	intensity	intensity	high to low	medium	high to low	medium	
intensity			intensity	intensity	intensity	intensity	
intervention							
0.80	1.09	1.08	1.10	1.08	1.11	1.09	
0.85	1.08	1.06	1.08	1.07	1.09	1.08	
0.90	1.06	1.05	1.06	1.05	1.07	1.06	
0.95	1.04	1.03	1.04	1.03	1.04	1.04	
MINIMAL RISK	N=1500 total (750 low		N=1225 total (N=1000 total (500 low		
STRATUM	intensity, 500 medium		intensity, 410		intensity, 333 medium		
	intensity, 250 high intensity)		intensity, 200 high intensity)		intensity, 167 high intensity)		
SVR in PWID	RR comparing	RR comparing	RR	RR comparing	RR	RR comparing	
receiving low	high to low	medium to low	comparing	medium to low	comparing	medium to low	
intensity	intensity	intensity	high to low	intensity	high to low	intensity	
intervention			intensity		intensity		
0.80	1.10	1.08	1.11	1.08	1.12	1.09	
0.85	1.08	1.06	1.09	1.07	1.09	1.08	
0.90	1.06	1.05	1.07	1.05	1.07	1.06	
0.95	1.04	1.03	1.04	1.03	1.05	1.04	

Table 15.4.1. Relative risk (RR) of sustained virologic response (SVR) across stratum of risk for treatment failure (elevated and minimal risk).

[figure not shown]
Based on preliminary data, minimal and elevated risk strata will be defined by the median of the prognostic score (estimated 1500 per stratum). However, the exact distribution will be based on the cutoff that maximizes predictive accuracy according to AUROC analysis. As such, an estimated 1000-1500 persons will be within the stratum that has the lower number of participants. **Table 15.4.1** illustrates the minimal detectable relative risks (RR) that can be detected for a range of scenarios assuming a two-sided alpha=0.05 and 80% power. The scenarios illustrate detectable effect sizes with the optimal sample size (n=3000) but also with a reduced total sample size of 2450 (assuming 1000-1225 will still be allocated per stratum).

For example, in the elevated risk stratum, assuming an SVR of 85% in those receiving the low/medium intensity intervention, a RR of 1.06 comparing SVR in those receiving the high intensity intervention to those receiving the medium intensity intervention and 1.08 comparing those receiving the high intensity intervention to those receiving the low intensity intervention can be detected if the total allocated to this stratum is 1500. Power will be slightly reduced if the total sample size in this stratum is 1000. Similarly, in the minimal risk stratum, if a 95% SVR rate is observed in those receiving the low intensity intervention, a RR of 1.03 comparing the medium intensity to the low intensity intervention and a RR of 1.04 comparing the high intensity intervention to the low intensity intervention can be detected with a sample size of 1500 per stratum. Power will be increased if a lower SVR (<95%) is observed in the comparator group.

If no difference is detected in a comparison of two arms, non-inferiority will be established if SVR in those receiving one intensity of intervention compared to another is less than 3.4% (non-inferiority with sample size of 1500 and SVR=95% in the comparison group). The margin is 4.5% if the sample size is 1000 in one of the groups. Non-inferiority margins <5% are clinically meaningful. Power for secondary outcomes of treatment completion is comparable.

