At the Entry visit, prior to randomization and treatment initiation, each participant will undergo a short survey to capture information on barriers/facilitators to treatment adherence identified in the prediction model. Responses to this survey will be captured in an eCRF and integrated with other data from the EHR. The algorithm will be used to classify persons into two strata according to their propensity for HCV treatment failure (minimal or elevated risk).

Individuals will be preferentially randomized to the support level that matches their failure risk. Those at elevated risk for treatment failure will be randomized at an allocation ratio of 3:2:1 for high, medium and low intensity support respectively. Those at minimal risk will be randomized at a ratio of 1:2:3 to high, medium and low-intensity support, respectively.

Randomization will be integrated into the EHR. The Study Nurse who will complete the survey will receive the determination of study arm from an automated program. Both study staff and study participants will be blinded to the designation of minimal/elevated risk stratum.

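### Section 15.4 says power rises if comparator SVR is below 95%, but on the plan's relative-risk scale it falls from 80% to about 38–41% at SVR 90%; the power lost with 1000 in a stratum is also understated

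*Protocol*

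**What the plan says.** Protocol section 15.4 works on the relative-risk scale. Table 15.4.1 "illustrates the minimal detectable relative risks (RR) that can be detected for a range of scenarios", "assuming a two-sided alpha=0.05 and 80% power", for comparator SVR of 0.80, 0.85, 0.90 and 0.95 and for strata of 1500, 1225 and 1000. The text below the table then picks out examples.

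- **Elevated-risk stratum, comparator SVR 85%, N=1500:** detectable RR 1.06 (high versus medium) and 1.08 (high versus low). For the smaller stratum it says: "Power will be slightly reduced if the total sample size in this stratum is 1000". No figure is attached.
- **Minimal-risk stratum, comparator SVR 95%, N=1500:** detectable RR 1.03 (medium versus low) and 1.04 (high versus low). The next sentence is: "Power will be increased if a lower SVR (<95%) is observed in the comparator group". It does not say what is held constant.

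The primary analysis (Protocol 15.7.2.1 and SAP section 1) also reports an RR, from log-binomial or Poisson models.

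**The concern.** The sentence on lower SVR follows directly after two RRs, so the natural reading is that power for those RRs improves. In Table 15.4.1 the minimal-risk column at N=1500 runs the other way. As comparator SVR goes from 0.95 through 0.90 and 0.85 to 0.80, the RR needed for 80% power goes 1.03, 1.05, 1.06, 1.08 (medium versus low) and 1.04, 1.06, 1.08, 1.10 (high versus low). If a larger RR is needed for the same power, the same RR must have less power.

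A comparator SVR below 95% is plausible. The table plans for it, and the primary analysis counts missing outcomes as failures. A reader who relied on the sentence would think the trial better powered in that range when, for the effects quoted, it is much weaker, and could then read a null comparison as evidence of no benefit. A stratum of 1000 is also within the plan's range, since section 15.4 expects 1000–1500 in the smaller stratum.

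**Working it through.** **Inputs.** Two-sided alpha 0.05 and 80% power (15.4). Elevated stratum: "N=1500 total (750 high intensity, 500 medium intensity, 250 low intensity") and "N=1000 total (500 high intensity, 333 medium intensity, 167 low intensity"). Minimal stratum: "Those at minimal risk will be randomized at a ratio of 1:2:3 to high, medium and low-intensity support, respectively" (15.5), which gives 250/500/750 at N=1500.

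**Formula.** Two independent proportions with pooled null variance and no continuity correction. Let p0 and n0 be the comparator SVR and arm size, p1 = RR × p0 and n1 those of the more intensive arm, d = p1 − p0, and p̄ the size-weighted mean of p0 and p1. Then

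s0 = √[p̄(1−p̄)(1/n0 + 1/n1)], s1 = √[p0(1−p0)/n0 + p1(1−p1)/n1], power = Φ[(d − 1.96·s0)/s1].

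**Step 1: reproduce the plan.** Solving for the RR at 80% power matches 47 of the 48 cells of Table 15.4.1 to two decimals. The exception is elevated stratum, high versus medium, N=1000, SVR 0.85: 1.0745 computed, 1.08 printed. For N=1225 I took the largest arm as 1225 − 410 − 200 = 615, as that entry is incomplete in the text I had. Arcsine, continuity-corrected, unpooled and log-RR versions match fewer cells (40, 37, 26 and 25).

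**Step 2: lower the comparator SVR (minimal stratum, N=1500).** I start from the unrounded RRs, so that power is exactly 80% at SVR 95%: 1.0317 (medium versus low) and 1.0392 (high versus low).

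Example, medium versus low at SVR 0.90: p1 = 0.90 × 1.0317 = 0.9285, d = 0.0285, p̄ = 0.9114, s0 = 0.01640, s1 = 0.01590. Power = Φ[(0.0285 − 0.0322)/0.01590] = Φ(−0.23) = 41%.

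| Held fixed | SVR 0.95 | 0.90 | 0.85 |
|---|---|---|---|
| RR 1.0317, medium (500) vs low (750) | 80% | 41% | 27% |
| RR 1.0392, high (250) vs low (750) | 80% | 38% | 25% |
| +3.01 points (0.95 × 0.0317), medium vs low | 80% | 45% | 32% |
| +3.73 points (0.95 × 0.0392), high vs low | 80% | 42% | 30% |

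With the printed RRs the picture is the same: RR 1.03 gives 74%, 37% and 24%, and RR 1.04 gives 82%, 39% and 25%. Their starting values differ from 80% only because the RRs are rounded. All five versions of the formula give the same direction.

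**Step 3: other scales.** RR 1.03 at SVR 0.95 means p1 = 0.9785, an odds ratio of (0.9785/0.0215)/(0.95/0.05) ≈ 2.4. Holding that odds ratio at SVR 0.90 gives p1 ≈ 0.956, and power rises from 74% to 96%. Holding the relative reduction in failures (2.85/5 = 57%) gives 97%. Holding treated-arm SVR at 97.85% gives above 99%.

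**Step 4: stratum of 1000 (elevated, SVR 85%).** The unrounded RRs with 80% power at N=1500 are 1.0621 (high versus medium) and 1.0755 (high versus low).

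- High (500) versus medium (333): d = 0.85 × 0.0621 = 0.0528, s0 = 0.02285, s1 = 0.02363. Power = Φ[(0.0528 − 0.0448)/0.02363] = Φ(0.34) = 63%.
- High (500) versus low (167): d = 0.85 × 0.0755 = 0.0642, s0 = 0.02704, s1 = 0.03034. Power = Φ[(0.0642 − 0.0530)/0.03034] = Φ(0.37) = 64%.

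The loss is 16–17 points. Starting each of the other formulas at its own 80%, power at N=1000 is 62–63%.

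**The case against.** The best defence is that the sentence does not say what is held fixed, and near a ceiling a failure-based reading is natural. Step 3 shows that power does rise on such scales. The table can be read the same way: for medium versus low, RR 1.03 at SVR 0.95 needs a 57% cut in failures (2.85/5), while RR 1.08 at 0.80 needs 32% (6.4/20). This stands as a possible intention. It does not rescue the text, because neither document names such a scale and the sentence comes straight after two RRs. That a lower SVR leaves room for larger effects is also true, but it is a different statement from more power for the RRs quoted.

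It is also fair that *slightly* is a judgement word and that Table 15.4.1 shows the N=1000 detectable RRs (1.08 and 1.09, against 1.06 and 1.08). A careful reader can recover the facts. The reader cannot easily see that a movement of 0.01–0.02 in RR costs 16–17 points of power.

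Four stronger readings are tempting and are not supported:

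- **That SVR below 95% is the likely case.** The 88% in Protocol 7.1.8 is treatment completion, not SVR, in a 50-person trial of other regimens. It makes lower SVR plausible and no more.
- **That readers are also misled about non-inferiority power.** The sentence closes the superiority paragraph. The non-inferiority paragraph states its 3.4% margin for SVR of 95%, and power figures would need a one-sided level that neither document gives.
- **That power at N=1000 is about 60% and 70%.** Those values start from the rounded RRs 1.06 and 1.08, whose power at N=1500 is 77% and 85%. The apparent gap between the two comparisons is mostly rounding.
- **That the table or the sample size is wrong.** The table reproduces, apart from one cell that differs by 0.01.

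**Conclusion.** The statement on lower SVR is wrong on the scale that the plan uses for its sample size and primary analysis, and also for a fixed absolute difference. Power of 80% at SVR 95% becomes about 38–41% at 90% and 25–27% at 85% for the same RR. The description of the N=1000 stratum understates a fall from 80% to about 63–64%.

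These figures rest on the unadjusted two-proportion formula that reproduces the table, on the stated arm sizes, and on SVR as analysed with no further inflation for dropout. Site adjustment is not modelled. The error lies in the power narrative. No sample size, allocation or analysis depends on either sentence, and the SAP contains no sample-size calculation that repeats them.

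**What to change.** In Protocol section 15.4:

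1. Replace the sentence on lower SVR with one to this effect: *for a fixed RR or a fixed absolute difference, power falls as comparator SVR falls, and the detectable RR rises as shown in Table 15.4.1.* Add the power at SVR 0.90 and 0.85 for the RRs detectable at 0.95: about 41% and 27% (medium versus low), 38% and 25% (high versus low).
2. If a failure-based effect was intended, name the scale (odds ratio, relative reduction in failures, or treated-arm SVR) and give the power on it.
3. Replace the description of the loss at a stratum of 1000 with the figures: from 80% to about 63% (high versus medium) and 64% (high versus low).

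The cost is two sentences and a handful of recomputed figures. The stated power becomes less favourable. Table 15.4.1, the design and the analysis need no change because of this point.

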Non-inferiority analyses. Additionally, while the overall trial is designed to assess superiority, if there is a failure to identify that one support intervention is superior to another, sensitivity analyses will examine non-inferiority particularly within the minimal risk stratum using a prespecified non-inferiority margin (i.e., that among those at minimal risk for treatment failure, the low intensity intervention is non-inferior to the medium and high-intensity interventions).

Subgroup and Exploratory Analyses. These are described in the Statistical Analysis Plan.

15.7.2.2. Secondary outcomes.

Secondary outcomes are 1) treatment completion defined as completing the prescribed course of treatment (12/24 weeks); 2) self-reported adherence; 3) reinfection defined as testing positive for HCV Core Ag after achieving SVR; and 4) HIV viral suppression defined as HIV RNA<LLOQI.

Treatment completion (secondary outcome). Those who prematurely discontinue treatment or are lost-to-follow-up prior to the completion of this visit will be considered as failures for this analysis. Using a log-binomial or poisson regression model (due to the high prevalence of the outcome), with adjustment for site, in the elevated risk stratum, the proportion completing treatment in those who received the low or moderate intensity interventions will be compared to those who received the high intensity intervention (in separate models) resulting in a relative risk (RR). For those at minimal risk of failure, analyses will be similar.

Sensitivity analyses. Sensitivity analyses similar to the primary outcome are described in the Statistical Analysis Plan.

Non-inferiority analyses. As with the primary outcome, if there is a failure to identify that one support intervention is superior to another, sensitivity analyses will examine non-inferiority particularly within the minimal risk stratum using a pre-specified non-inferiority margin (i.e., that among those at minimal risk for treatment failure, the low intensity intervention is non-inferior to the medium and high-intensity interventions).

Subgroup analyses. These are described in the Statistical Analysis Plan.

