complete the SVR visit within the window including both those who are lost to follow-up before and after treatment completion. We will conduct an additional per protocol analysis which will exclude individuals who died prior to SVR assessment and who are alive but lost to follow-up (i.e., do not complete the SVR visit) but account for the informative loss to follow-up using inverse probability of censoring weights. Further, we will include the randomization to the different intervention arms as an instrumental variable. An instrumental variable analysis estimates the "complier" average treatment effect. Therefore, by using the randomization as an instrumental variable for the treatment arms, we would be able to estimate the complier treatment effect for those that fully comply with the intervention.

- A second approach will use fully conditional multiple imputation of the SVR outcome based on only two variables: treatment completion and adherence. In this analysis, undetermined SVR due to death will not be imputed; deaths will be treated as SVR failures.
- Assessing the relationship of the treatment arms with loss to follow-up is also of interest in and of itself. This is because as an implementation strategy, policy makers would need to know the potential for loss to a program that they are implementing. Therefore, a time to lost to follow-up analysis will be examined using standard survival methods and accounting for prognostic score.
- **1c. Non-inferiority analyses**. While the overall trial is designed to assess superiority, if there is a failure to identify that one support intervention is superior to another in the minimal risk stratum, sensitivity analyses will examine non-inferiority within this stratum. Non-inferiority is of interest in this case because it is possible that the additional interventions confer no benefit beyond what is offered by the low intensity intervention among those at minimal risk of failure this has important implications for costs and programs. The non-inferiority margin is 5% which is also clinically meaningful.

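### Section 15.4 gives one non-inferiority figure per stratum size for any two arms, but 3.4% and 4.5% fit only low versus medium intensity, and only roughly; low versus high needs wider margins

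*Protocol*

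**What the plan says.** Protocol section 15.4 sizes the trial for superiority and tabulates detectable relative risks separately for each arm pair, "assuming a two-sided alpha=0.05 and 80% power". It then turns to non-inferiority. "If no difference is detected in a comparison of two arms", non-inferiority is to be established if the difference in SVR "is less than 3.4% (non-inferiority with sample size of 1500 and SVR=95% in the comparison group"). The next sentence reads "The margin is 4.5% if the sample size is 1000 in one of the groups". Neither sentence names the arm pair, the alpha or the power.

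The arms are not equal. Section 15.5 states: "Those at minimal risk will be randomized at a ratio of 1:2:3 to high, medium and low-intensity support, respectively". Table 15.4.1 puts the minimal-risk arms at 750 low, 500 medium and 250 high for N=1500, and at 500, 333 and 167 for N=1000.

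Protocol section 15.7.2.1 names the claim to be tested: "that among those at minimal risk for treatment failure, the low intensity intervention is non-inferior to the medium and high-intensity interventions". SAP section 1c keeps non-inferiority to the minimal-risk stratum and says: "The non-inferiority margin is 5% which is also clinically meaningful". The SAP does not use 3.4% or 4.5%.

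**The concern.** With 1:2:3 allocation, low versus high rests on a comparison arm half the size of the one in low versus medium. A single figure per stratum size cannot serve both pairs. Someone using section 15.4 would take low versus high to be as well supported as low versus medium.

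Both figures are also anchored at 95% SVR, the most favourable row of Table 15.4.1 for an absolute margin. The table plans for 80% to 95%. The primary analysis counts deaths and losses to follow-up as failures, which would lower the analysed SVR if the non-inferiority analysis uses the same rule.

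At stake is the conclusion that minimal-risk clients can do without the most intensive support. The SAP itself says this bears on costs and programmes. If the comparison is under-powered, a failure to show non-inferiority says little, yet could be taken as a sign that intensive support is needed.

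**Working it through.** **Inputs.** Arm sizes are from Table 15.4.1. For N=1225 the table gives 410 and 200, leaving 615 for the largest arm. SVR is 80% to 95%, from the same table. Two assumptions are mine: true SVR is equal in both arms, and the section's two-sided 0.05 (one-sided 0.025) and 80% power carry over to non-inferiority. As a check on the inputs, the pooled two-proportion formula reproduces the superiority relative risks in Table 15.4.1 to rounding, a few cells only with a continuity correction.

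**Formulas.** SE = sqrt[p(1-p)(1/n1 + 1/n2)].
- Wald: margin = (1.960 + 0.842) x SE = 2.802 x SE; power at margin m = Phi(m/SE - 1.960).
- Farrington-Manning (score test): power = Phi[(m - 1.960 x SE0)/SE], where SE0 uses the restricted maximum-likelihood rates under a true deficit of m in the low arm.

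**The printed figures against low versus medium, SVR 95%.**
- N=1500: SE = sqrt[0.0475(1/750 + 1/500)] = 0.01258; margin 3.53 points (score 3.49); printed 3.4.
- N=1000: SE = sqrt[0.0475(1/500 + 1/333)] = 0.01542; margin 4.32 points (score 4.30); printed 4.5.

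These are close but not exact. Wald power at the printed figures is 77.1% and 83.1%. No variant tried gives both printed figures for one pair.

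**Low versus high, SVR 95%.**
- N=1500: SE = sqrt[0.0475(1/750 + 1/250)] = 0.01592; Wald margin 4.46, score 4.05. Power at 3.4 points: Phi(0.034/0.01592 - 1.960) = 57.0%; score 66.1%.
- N=1000: SE = sqrt[0.0475(1/500 + 1/167)] = 0.01948; Wald margin 5.46, score 4.93. Power at 4.5 points: Phi(0.045/0.01948 - 1.960) = 63.7%; score 73.1%.

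Exact binomial power at the printed figures is 58.7% (Wald) and 66.4% (score) at N=1500, and 66.6% and 75.6% at N=1000. All are below 80%.

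**The more lenient one-sided 0.05, which the documents do not state.** Low versus high then needs 3.63 to 3.96 points at N=1500, so 3.4 is still missed. At N=1000 it needs 4.41 (score) to 4.84 (Wald). The 4.5 figure is therefore about reached with a score test (81% by formula, 83.3% exact) or by exact Wald power (79.7%), but not by the Wald formula (74.7%).

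**Power at the SAP's 5-point margin, one-sided 0.025 (Wald to score, %).**

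| Pair | N | SVR 95% | SVR 90% | SVR 85% | SVR 80% |
|---|---|---|---|---|---|
| Low vs high | 1500 | 88.1-92.7 | 62.6-69.6 | 48.3-53.5 | 40.2-43.8 |
| Low vs high | 1225 | 80.5-87.3 | 53.5-61.2 | 40.5-45.7 | 33.6-37.1 |
| Low vs high | 1000 | 72.8-81.0 | 46.2-53.8 | 34.7-39.6 | 28.7-32.0 |
| Low vs medium | 1500 | 97.8 | 82.3-83.5 | 67.9-69.4 | 58.1-59.4 |
| Low vs medium | 1225 | 94.8-94.9 | 74.3-75.8 | 59.3-60.9 | 50.0-51.3 |
| Low vs medium | 1000 | 89.9-90.0 | 65.4-67.1 | 50.8-52.4 | 42.4-43.6 |

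An exact 3:1 split at N=1225 (613 versus 204) changes the low-versus-high row only slightly, to 81-88% at SVR 95% and 54-62% at SVR 90%. At one-sided 0.05 the best low-versus-high cell at SVR 90% (score test, N=1500) is 78.7%, still under 80%.

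**The case against.** The strongest reply is that section 15.4 states neither power nor alpha for non-inferiority. The 80% and two-sided 0.05 are attached to the superiority table, so one cannot say that the plan promises 80% power for low versus high and fails to deliver it. That stands: the shortfall is conditional on carrying those values over. The mismatch between one printed figure and two unequal pairs does not depend on it.

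Second, the SAP's 5-point margin softens the consequence. At SVR 95%, low versus high is adequately powered at N=1500 and reaches about 80% or more at N=1225; at N=1000 it is borderline, above or below 80% depending on the test. Also, 95% is disclosed in the sentence and is the protocol's own worked example for the minimal-risk stratum. This stands too, but only at that SVR. At 90% or lower no method tried brings low versus high to 80% at 5 points.

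Third, non-inferiority is a lesser objective handled as a sensitivity analysis, and nothing in the plan proposes reading a failed test as support for intensive care. That limits the weight of the point without removing it.

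Two stronger readings should be resisted. A reader might infer that the trial's sample size is wrong; the superiority figures reproduce and are unaffected. A reader might also infer that low versus high alone is weak; low versus medium falls below 80% as well once SVR is lower.

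**Conclusion.** The point holds as a matter of how section 15.4 reports non-inferiority. The printed 3.4% and 4.5% are offered for any two arms but roughly describe low versus medium only. At one-sided 0.025 and 80% power, low versus high needs about 0.65 to 1.06 points more than printed at N=1500 (4.05 - 3.4; 4.46 - 3.4) and 0.43 to 0.96 more at N=1000 (4.93 - 4.5; 5.46 - 4.5).

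At the SAP's margin the practical gap depends on SVR. Low versus high is under 80% in every cell at SVR 90% or lower, and at N=1000 and SVR 95% with a Wald test. Low versus medium is under 80% at SVR 85% or lower for N=1500 and at 90% or lower for N=1000, at either one-sided alpha; for N=1225 at SVR 90% it depends on the alpha.

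This rests on equal true SVR in both arms, on the table's arm sizes, and on the alpha and power carried over from the superiority table. It should be corrected. It does not threaten the primary analysis, and it does not settle which document's margin governs.

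**What to change.** In section 15.4, and by reference in SAP section 1c:

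- Replace 3.4% and 4.5% with a table of power at the SAP's 5-point margin, for low versus medium and low versus high separately, at SVR 0.80, 0.85, 0.90 and 0.95 and stratum sizes 1000, 1225 and 1500. Name the test and the one-sided alpha.
- Identify every cell under 80%, for both pairs.
- Say that for a fixed absolute margin power falls as SVR falls. The section's remark that power rises at lower SVR belongs to the superiority paragraph and should not be carried across.
- For under-powered cells, commit to reporting the difference with its confidence interval, and state that a failed non-inferiority test will not be read as evidence that more intensive support is needed.

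The cost is one recalculated table and a few sentences. No participants are added and the design does not change; the stated non-inferiority prospects become less favourable.
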